8.1.7. Adverse Events of Interest

Adverse events of interest (AEIs) include infections, gastrointestinal perforations, herpes zoster, malignancies (excluding non-melanoma skin cancers), non-melanoma skin cancers, and thromboembolic events. Summaries of the following treatment-emergent AEIs will be produced to enhance the analysis of safety data.

- Events of infection presented in the following subcategories:
 - AEs of infections, utilizing all AEs in the MedDRA Infections and Infestations SOC
 - AEs of serious infections, using all AEs in the MedDRA Infections and Infestations SOC that are classified as SAEs
 - AEs of herpes zoster, utilizing a MedDRA search term (MST) list developed by Gilead
 - AEs of opportunistic infections (OIs), using a Standardized MedDRA Query (SMQ)--narrow scope
 - Active tuberculosis, using a MST list developed by Gilead
 - Hepatitis B or C infections, using a MST list developed by Gilead
- AEs of malignancies, excluding non-melanoma skin cancers, utilizing a MST list developed by Gilead
- AEs of non-melanoma skin cancers, utilizing a MST list developed by Gilead
- AEs of gastrointestinal perforation, utilizing a MST list developed by Gilead
- AEs of arterial or venous thrombosis and/or thromboembolism, presented in the following subcategories:
 - AEs of venous thrombosis, utilizing a MST list developed by Gilead
 - AEs of pulmonary embolism, utilizing a MST list developed by Gilead
 - AEs of arterial thrombosis, utilizing the embolic and thrombotic events, arterial SMQ
 - AEs of cerebrovascular events, utilizing the ischaemic central nervous system vascular conditions SMQ

For the double-blind phase, the number of subjects with TE AEIs and SAEs, the corresponding PYE, the calculated EAIR, and the exact 95% CIs (defined in Section 8.1.5.3) will be summarized for each treatment group by PT. The EAIR difference (Filgotinib 200 mg – Placebo) and corresponding 95% CIs for the difference between treatment groups (specified in section 8.1.5.3) will also be presented for the double-blind phase of the study.

For the overall study, the number of subjects with TE AEIs and SAEs, the corresponding PYE, the calculated EAIR, and the exact 95% CIs (defined in Section 8.1.5.3) will be summarized for each treatment (filgotinib and placebo) by PT for each AEI category and separately for SAEs. Filgotinib group will include filgotinib to open-label filgotinib treatment sequence plus the filgotinib exposure for filgotinib to SOC treatment sequence and those randomized to filgotinib who did not continue to extension phase. Placebo will include the placebo to SOC treatment sequence and those randomized to placebo who did not continue to extension phase.

Data listings for each AEI will also be provided.

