4.2.1. Duration of Exposure to Study Drug

Total duration of exposure to double-blind study drug (in weeks) will be defined as: $([\text{last dosing date of double-blind study drug minus first dosing date of double-blind study drug plus 1}] \text{ divided by 7})$, regardless of any temporary interruptions in study drug administration. Results for all calculations of duration will be displayed to 1 decimal place (eg, 4.5 weeks).

Total duration of exposure to open-label filgotinib study drug (in weeks) will be defined as: $([\text{last dosing date of open-label filgotinib study drug minus first dosing date of open-label filgotinib study drug plus 1}] \text{ divided by 7})$, regardless of any temporary interruptions in study drug administration.

Total duration of exposure to any filgotinib study drug (in weeks) will be defined as: $([\text{last dosing date of any filgotinib study drug minus first dosing date of any filgotinib study drug plus 1}] \text{ divided by 7})$, regardless of any temporary interruptions in study drug administration.

For subjects who took double-blind placebo and then switched to standard of care in extension phase; and subjects who took double-blind filgotinib, were a non-responder at Week 13, and switched to standard of care in extension phase, the duration in the extension phase will be calculated as last date in extension phase minus first date in extension phase + 1 divided by 7 (eg, reported in weeks to 1 decimal place).

For subjects with a partial last dosing date (ie, month and year of last dose are known), the latest of the dispensing dates of study drug bottles, study drug start dates and end dates, and the imputed last dosing date (day imputed as 15) will be used as the final imputed last dosing date. If the subject died and the death date is complete (ie, not partial date) and before the imputed last dosing date, the complete death date will be used as the imputed last dosing date.

If only year is recorded (ie, month and day of last dose are missing), the latest of the dispensing month of study drug bottles, study drug start month, and study drug end month will be used to impute the unknown last dose month. If the subject died and the death date has month and year available and before the imputed last dose month, then the month of death will be used instead. With the month imputed, the aforementioned method will be used to impute the last dose date.

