8.1.5.3. Analysis of Exposure-Adjusted Incidence Rate

The Exposure-Adjusted Incidence Rate (EAIR) for a TEAE is defined as:

$$\text{Incidence rate per 100 patient years of exposure (PYE)} \\ = \frac{\text{Total number of subjects with an event}}{\text{Total PYE}} \times 100.$$

The total patient-years of exposure (PYE) to a treatment is the sum of the individual subject's PYE and is defined as:

For subjects with an event:

$$\text{PYE} = (\text{Event start date} - \text{first date in DB phase} + 1) / 365.25$$

For subjects with no event:

$$\text{PYE} = (\text{Calculation end date} - \text{first date in DB phase} + 1) / 365.25$$

where calculation end date for the double blind phase = the earliest date among

(last dosing date of double blind phase +30, first date in extension phase of the study -1 day, death date, cutoff date). If the last study drug dosing date is missing and the subject has stopped drug, the latest date among study drug end date, clinical visit date, and laboratory sample collection date that occurred during the double-blind phase will be used.

where calculation end date for the entire study display = the earliest date among

(last dosing date of OL filgotinib+ 30 days [subjects in the filgotinib to OL filgotinib sequence who permanently discontinued OL filgotinib]; last dosing date of double-blind filgotinib [subjects in the filgotinib to standard of care group], last date on standard of care in extension phase [subjects in placebo to standard of care sequence who switched to monitoring phase or early terminated from study after starting extension phase], last dosing date of double-blind study drug + 30 for subjects who did not start extension phase, data cutoff date, death date).

If event start date during the double-blind phase is partially missing and the non-missing portion matches the first dosing date (month and/or year) of double-blind study drug; or if the date is completely missing, AE onset is imputed as the date of first dose of double-blind study drug. Otherwise it is imputed as the first day of the month (if only day is missing) or January 1st of the year (if day and month are missing).

The exact 95% CI based on the Poisson distribution [{Ulm 1990}](#) for EAIR is defined as:

$$\left(\frac{\chi^2_{2(\text{Total number of subjects with an event}), 0.025}}{2 \times \text{Total PYE}}, \frac{\chi^2_{2(1+\text{Total number of subjects with an event}), 0.975}}{2 \times \text{Total PYE}} \right) \times 100.$$

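### The overall-study safety rates call placebo a group whose counted time is placebo followed by open-label standard of care

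*SAP*

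**What the plan says.** SAP 8.1.7 plans two sets of exposure-adjusted rates. The double-blind set compares the randomized groups and includes a rate difference with a confidence interval. The overall-study set has two groups, filgotinib and placebo, and no difference is planned. Its placebo group is defined thus: "Placebo will include the placebo to SOC treatment sequence and those randomized to placebo who did not continue to extension phase". Its filgotinib group takes the filgotinib-to-open-label sequence, "plus the filgotinib exposure for filgotinib to SOC treatment sequence", and filgotinib subjects who did not enter the extension.

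SAP 8.1.5.3 sets the denominator: "The total patient-years of exposure (PYE) to a treatment is the sum of the individual subject's PYE". The clock starts at the first double-blind date and stops at the first event or at a calculation end date. For the whole-study display the end dates differ by group:

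- filgotinib switchers: "last dosing date of double-blind filgotinib [subjects in the filgotinib to standard of care group";
- non-entrants: "last dosing date of double-blind study drug + 30 for subjects who did not start extension phase";
- placebo switchers: the last standard-of-care date, but only for "subjects in placebo to standard of care sequence who switched to monitoring phase or early terminated from study after starting extension phase".

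Elsewhere the SAP keeps placebo and standard of care apart. SAP 3.2 groups extension safety events by sequence, with placebo to standard of care as a named sequence. SAP 4.2.1 reports standard-of-care time separately: "the duration in the extension phase will be calculated as last date in extension phase minus first date in extension phase". Protocol 3.1 states that placebo subjects entering the extension move to standard of care.

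**The concern.** A rate headed placebo should describe time on placebo, or at least say that it does not. Here the denominator continues for up to 143 weeks of open-label treatment. The two columns also follow different rules: standard-of-care time is removed for filgotinib switchers and kept for placebo switchers.

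That time is not an untreated background. Protocol Table 5-1 bars TNF antagonists, interleukin antagonists and other JAK inhibitors during the extension only for subjects on open-label filgotinib, so a placebo switcher may receive them. The protocol's own background sections link such classes to events in this display: serious infection for TNF inhibitors (1.1.3), infection for JAK inhibition (1.4) and thrombosis for another JAK inhibitor (1.1.1). On the other side, SAP 3.7.1 notes that some of this time is background medication alone or, rarely, no rheumatic medication while a new regimen is obtained. A reader who sets the long-term filgotinib rate beside this column could take it for a placebo reference, which it is not.

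Two smaller defects affect the same column. The event window and the person-time window for placebo switchers do not match, and SAP 8.1.5.3 gives no specific end date for those who complete Week 156.

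**Working it through.** **1. The plan's own figure.** Follow-up to Week 156 less 13 blinded weeks is 156 − 13 = 143 weeks, the extension length in Protocol 3.6.

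**2. One event-free placebo switcher, on-time switch.** The standard-of-care share of counted time at Week W is (W − 13)/W:

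- Week 26: 13/26 = 50%
- Week 52: 39/52 = 75%
- Week 156: 143/156 = 92%

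**3. Late switch.** Assume blinded dosing runs to Day 112, the upper limit of the Week 13 semen window in SAP Table 3-4. The share is (7W − 112)/(7W): 70/182 = 38%, 252/364 = 69% and 980/1092 = 90%.

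**4. Whole column.** Let e be the fraction entering the extension and s the standard-of-care weeks of each entrant. Non-entrants contribute 91 + 30 days. The share is 7es / [91 + 30(1 − e) + 7es]. The documents do not give e, so 0.6 to 1.0 is assumed, with all entrants event-free and followed to the stated visit.

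| Visit | s | e = 0.6 | e = 1.0 |
|---|---|---|---|
| Week 26 | 13 | 54.6/157.6 = 35% | 50% |
| Week 52 | 39 | 163.8/266.8 = 61% | 75% |
| Week 156 | 143 | 600.6/703.6 = 85% | 92% |

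At e = 0.6 the share passes one half when 4.2s > 103, that is s > 24.5 weeks, near Week 38.

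**5. Direction.** Suppose, purely for illustration, a placebo rate of 10 per 100 patient-years and a standard-of-care to placebo rate ratio r. At Week 156 the on-time switcher mixture reads 10 × [91/1092 + r(1 − 91/1092)]. This is 5.4 for r = 0.5 and 19.2 for r = 2. Neither the base rate nor r is in the documents, and the distortion can go either way.

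**6. Apparent precision.** For 100 placebo subjects who all enter the extension and have no event, the SAP's exact Poisson upper limit is 3.689 divided by the patient-years. On placebo time alone, 100 × 91/365.25 = 24.9 patient-years, giving 14.8 per 100 patient-years. With standard-of-care time included, the patient-years are 49.8, 99.7 and 299.0 at Weeks 26, 52 and 156, giving 7.4, 3.7 and 1.2. The narrowing comes entirely from time not on placebo.

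**7. Windows for placebo switchers.** SAP 8 includes extension safety data to 30 days after the last standard-of-care date. The treatment-emergent bullet in SAP 8.1.5.1 gives an end date only for open-label filgotinib. The worked example below it, which opens with a placebo subject and then speaks of filgotinib, runs to 30 days after standard of care. SAP 8.1.5.3 stops person-time at the last standard-of-care date, with no tail. A Week 156 completer has only data cutoff or death in that list, although SAP 3.7.1 already defines a last standard-of-care date for such subjects.

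**8. Windows for filgotinib switchers.** SAP 3.7.1 starts their extension the day after the last double-blind dose. SAP 8.1.5.1 closes double-blind events the day before the extension starts. SAP 8.1.5.3 stops person-time at the last double-blind dose. These three agree.

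**The case against.** The best defence is that nothing is hidden. SAP 8.1.7 states who is in the group, the randomized placebo rate has its own display, extension events are tabulated under the correct sequence name, and no overall-study difference is computed. Subjects never given filgotinib form a coherent group. The table shells are not in the documents, so the printed heading is inferred from the two group names in SAP 8.1.7. All of this stands and limits the point to labelling and interpretation. It does not rescue the label, because tables are read without the SAP beside them.

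A reader might infer more than the documents support:

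- *That the column is mostly standard of care as soon as follow-up passes Week 26.* At 60% entry that happens only near Week 38. The 92% is for one event-free subject followed to Week 156, and person-time stops at a first event.
- *That the filgotinib column also mismatches events and time, and that switchers should be carried 30 days further.* Step 8 shows agreement. The 30-day window in Protocol 8.5.6 is longer, so 30 of 121 days (25%) per switcher fall outside the filgotinib rate. However, Protocol 8.5.4 allows exceptions, the double-blind display makes the same cut in both arms ("first date in extension phase of the study -1 day"), and adding those days would put standard-of-care time into the filgotinib column.
- *That the window mismatch makes placebo-switcher person-time short by a calculable percentage.* Protocol 7.3 collects adverse events until the last study visit and, in the Monitoring Phase, only serious and procedure-related ones. A further 30 days would often be time without full collection.
- *That completers would accumulate large amounts of unobserved time.* This depends on the gap between last visit and cutoff, which the documents do not give.

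**Conclusion.** The point holds as one of labelling and missing separation in the overall-study display, and it should be corrected. The column is a placebo-then-standard-of-care mixture and should not be read as a placebo rate. The per-switcher shares rest only on the 13-week phase and an on-time switch. The column shares rest on assumed entry and full follow-up of entrants, and early departures or events would lower them. Any effect on how filgotinib appears is of unknown sign and size, because the documents give no standard-of-care mix, entry rate or event rates. The mismatched windows and the undefined end date for completers are real but small. The randomized double-blind rates and their difference are untouched.

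**What to change.** In SAP 8.1.5.3 and 8.1.7, for the overall-study display only:

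1. Title the column *Placebo then standard of care*. Add a standard-of-care-period rate whose clock starts at the extension start date in SAP 3.7.1 and which counts each subject's first event within that period, whether or not he had one earlier. The existing double-blind rate serves as the placebo-period rate.
2. For placebo switchers, end both events and person-time at the last standard-of-care date in SAP 3.7.1, including Week 156 completers. Subjects still in the extension at an interim analysis stay at the data cutoff.
3. Leave filgotinib switchers at the last double-blind dose. Footnote that events in the following 30 days are reported in the extension tables by sequence.

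The cost is SAP wording, one added derivation and one footnote, with no new data. Retitling alone costs nothing. The drawback is that events in the 30 days after standard of care leave this display, though they remain in the extension tables. The placebo-period rate will have a wider interval than the mixture, which reflects how little placebo time there is.

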8.1.7.1. Cardiovascular Event Adjudication Committee

An independent cardiovascular event adjudication committee (CVEAC) reviews and adjudicates all potential MACE and thromboembolic events in a blinded manner. To identify potential MACE and thromboembolic events, the following AEs will be sent for adjudication. Please refer to the Cardiovascular Event Adjudication Committee Charter for more details.

- All AEs leading to death
- CV events (meeting serious criteria), utilizing a MST list developed by Gilead
- MI, utilizing a narrow scope Standardized MedDRA Query (SMQ)
- Unstable angina (meeting hospitalization criteria), utilizing a MST list developed by Gilead
- Transient ischemic attack, utilizing a MST list developed by Gilead
- Stroke, utilizing a MST list developed by Gilead
- Cardiac failure (meeting hospitalization criteria), utilizing a MST list developed by Gilead
- Percutaneous coronary intervention, utilizing a MST list developed by Gilead
- Embolic and thrombotic events, utilizing a narrow scope SMQ

The CVEAC will review the above AEs, and related clinical data to adjudicate whether the criteria for MACE (CV death, MI, and/or stroke), ASTE, and VTE have been met for each AE.

The number and percentage of subjects with positively adjudicated TE MACE, TE ASTE, and TE VTE will be summarized by treatment group using the adjudicated category if applicable for the final analysis of the study only.

A by-subject listing for subjects with potential events for adjudication (MACE, ASTE, and VTE) and whether the event was positively adjudicated by CVEAC will be provided for each interim analysis and for the final analysis of the study.

A by-subject listing of thromboembolic history and risk factors will be provided for subjects with potential events for adjudication (MACE, ASTE, and VTE), if applicable.

8.2. Laboratory Evaluations

Laboratory data collected during the study will be analyzed and summarized using both quantitative and qualitative methods. Summaries of laboratory data during the double-blind phase of the study will be provided by double-blind treatment group for the Safety Analysis Set. Summaries of laboratory data during the extension phase of the study will be provided by treatment sequence for the Extension Phase Safety Analysis Set.

Analysis will be based on values reported in conventional units. When values are below the LOQ, they will be listed as such, and the closest imputed value will be used for the purpose of calculating summary statistics as specified in Section 3.7. Hemolized test results will not be included in the analysis, but they will be listed in by-subject laboratory listings.

A by-subject listing for laboratory test results will be provided by subject ID number and time point in chronological order for hematology, serum chemistry, and urinalysis separately. Values falling outside of the relevant reference range and/or having a severity grade of 1 or higher based on CTCAE criteria will be flagged in the data listings, as appropriate.

No formal statistical testing is planned.

8.2.1. Summaries of Numeric Laboratory Results

Descriptive statistics will be provided by treatment (double-blind treatment group for double-blind phase and by treatment sequence of extension phase) for selected laboratory tests as follows:

- Baseline values
- Values at each postbaseline time point
- Change from baseline at each postbaseline time point

A baseline laboratory value will be defined as the last measurement obtained on or prior to the date of first dose of double-blind study drug. Change from baseline to a postbaseline visit will be defined as the visit value minus the baseline value. The mean, median, Q1, Q3, minimum, and maximum values will be displayed to the reported number of digits; SD values will be displayed to the reported number of digits plus 1.

Median (Q1, Q3) change from baseline at each timepoint for selected laboratory tests will be plotted using a line plot by treatment (double-blind treatment for double-blind phase and treatment sequence for extension phase) and time point.

In the case of multiple values in an analysis window, data will be selected for analysis as described in Section 3.7.3.

8.2.2. Graded Laboratory Values

The CTCAE version 4.03 will be used to assign toxicity grades (0 to 4) to laboratory results for analysis. Grade 0 includes all values that do not meet the criteria for an abnormality of at least Grade 1. For laboratory tests with criteria for both increased and decreased levels, analyses for each direction (ie, increased, decreased) will be presented separately.

8.2.2.1. Treatment-Emergent Laboratory Abnormalities

Treatment-emergent laboratory abnormalities during the double-blind phase are defined as values that increase at least 1 toxicity grade from baseline at any postbaseline time point, up to the first dose date of open-label filgotinib/first date in extension phase (if non-missing) or to the date of last dose of double-blind study drug plus 30 days for subjects who permanently discontinued double-blind study drug (and did not continue to extension phase).

Treatment-emergent laboratory abnormalities during the extension phase are defined as values that increase at least 1 toxicity grade from baseline at any postbaseline time point after first dose date of open-label filgotinib/first date in extension phase to last dose date of open-label filgotinib/standard of care in extension plus 30 days or to the last available date in the database snapshot for subjects who were on extension phase treatment at the time of an interim analysis.

If the relevant baseline laboratory value is missing, any abnormality of at least Grade 1 observed within the time frame specified above will be considered treatment emergent.

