Follow-up (FU) Day will be calculated from last study drug (double-blind study drug or open-label filgotinib) dosing date or end date of extension phase for subjects on standard of care.

The FU day is derived as Assessment Date – Last Dose Date of study drug/end date of extension phase for subjects on standard of care

Therefore, Follow-up Day 1 is the first day after permanent discontinuation of all study drugs or end of Extension Phase for subjects on standard of care in extension phase.

Baseline is defined as the last available observation taken on or prior to the first dose date of double-blind filgotinib/placebo study drug.

For semen parameters, including sperm concentration, total sperm count, ejaculate volume, sperm total motility, and sperm morphology, the baseline value is the mean of 2 evaluable samples from the screening visit. The baseline value for sperm parameters is used to determine whether subjects have met a sperm parameter decrease threshold (ie, $\geq 50\%$ decrease from baseline in sperm concentration and/or motility and/or morphology).

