8.1.5. Treatment-Emergent Adverse Events

8.1.5.1. Definition of Treatment-Emergent Adverse Events

Treatment-emergent adverse events (TEAEs) during the double-blind phase are defined as 1 or both of the following:

- Any AEs with an onset date on or after the double-blind study drug start date through first dose date of open-label filgotinib/start date in extension phase minus 1 day (if subject enrolled in extension phase) or to last dose date of double-blind study drug + 30 days for subjects who permanently discontinue double-blind drug and do not enroll into extension phase (including subjects who meet a sperm decrease threshold who stop study drug and continue to be followed in the monitoring phase for reversibility)
- Any AEs leading to premature discontinuation of double-blind study drug

Treatment-emergent adverse events (TEAEs) during the extension phase are defined as 1 or both of the following:

- Any AEs with an onset date on or after first dose date of open-label filgotinib/first dose date in extension phase to last dose date of open-label filgotinib + 30 days for subjects who permanently discontinue open-label filgotinib (including subjects who meet a sperm decrease threshold who stop study drug and continue to be followed in the monitoring phase for reversibility) or all AEs for subjects who are ongoing on open-label filgotinib/standard of care in extension phase at the time of an interim analysis
- Any AEs leading to premature discontinuation of open-label filgotinib study drug

For example, for a subject who took double-blind placebo and switched to standard of care in the extension phase, TEAEs with an onset date on/after first dose date of double-blind filgotinib and prior to first date in extension phase will be TE for double-blind filgotinib (summarized with double-blind phase); from first date in extension phase up to last dose date of standard of care in extension phase + 30 days will be TE for standard of care (summarized by treatment sequence [double-blind filgotinib to standard of care] for the extension phase).

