8.2.2.2. Treatment-Emergent Marked Laboratory Abnormalities

Treatment-emergent marked laboratory abnormalities during the double-blind phase are defined as values that increase from baseline by at least 3 toxicity grades at any postbaseline time point, during double-blind phase. Treatment-emergent marked laboratory abnormalities during the extension phase are defined as values that increase from baseline by at least 3 toxicity grades at any postbaseline time point during extension phase.

If the relevant baseline laboratory value is missing, any Grade 3 or 4 values observed within the timeframe specified above will be considered treatment-emergent marked abnormalities.

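### Extension-phase treatment-emergent laboratory counts use the pre-study baseline, so an abnormality that arose in the double-blind phase and persists is counted again, in all three treatment sequences

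*SAP*

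**What the plan says.** SAP 3.7.1 sets the general rule: "Baseline is defined as the last available observation taken on or prior to the first dose date of double-blind filgotinib/placebo study drug". SAP 8.2.1 repeats it for laboratory data, as the "last measurement obtained on or prior to the date of first dose of double-blind study drug". No extension-phase baseline is defined.

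For the extension, SAP 8.2.2.1 counts "values that increase at least 1 toxicity grade from baseline at any postbaseline time point after first dose date of open-label" filgotinib or the first date in the extension phase. The window runs to the "last dose date of open-label filgotinib/standard of care in extension plus 30 days". SAP 8.2.2.2 defines marked abnormalities as "values that increase from baseline by at least 3 toxicity grades at any postbaseline time point during extension phase". Under SAP 8.2.2.3 each man is classified by his worst postbaseline grade, and extension results are shown by treatment sequence. SAP 3.2 lists three: filgotinib to open-label filgotinib, filgotinib to Standard of Care, and placebo to Standard of Care.

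Adverse events follow another rule. SAP 8.1.5.1 admits to the extension table "Any AEs with an onset date on or after first dose date of open-label filgotinib/first dose date in extension phase", so an event enters by its onset date.

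**The concern.** A man at grade 0 before the study who reaches grade 2 on blinded drug, and is still at grade 2 at his first extension sample, meets the definition in both phases although nothing new happened in the second. The extension table then mixes persisting abnormalities with new ones under one label. Someone reading the adverse event and laboratory tables side by side would take the term to mean the same in both. At stake is what can be said about abnormalities arising during long-term open-label filgotinib or Standard of Care.

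**Working it through.** The SAP states no figure to reproduce, so the check is to apply the rule to example courses and then see how far the count could move.

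**1. The rule applied to grades.** A man is emergent in a phase if any grade in that phase minus the baseline grade is at least 1. The alternative requires a grade above both the pre-study baseline and the last double-blind grade.

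| Course | Baseline | Double-blind | Extension | Emergent, double-blind | Emergent, extension (SAP) | Emergent, extension (both references) |
|---|---|---|---|---|---|---|
| Persists | 0 | 0, 1, 2 | 2, 2, 2 | yes | yes | no |
| Persists, then resolves | 0 | 0, 1, 2 | 2, 0, 0 | yes | yes | no |
| New in extension | 0 | 0, 0, 0 | 0, 1 | no | yes | yes |
| Worsens in extension | 0 | 0, 0, 1 | 2 | yes | yes | yes |
| Resolves before extension | 0 | 1, 2, 0 | 0, 0 | yes | no | no |

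Only the first two rows change. New onset and worsening are kept.

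**2. When the first extension sample falls.** For men on Standard of Care, SAP 3.7.1 starts the extension the day after the last blinded dose, and SAP 8.2.2.1 closes their double-blind window at that point. Filgotinib non-responders have a safety visit 30 days after the last dose, with hematology and chemistry (Protocol 3.1 and Appendix 2). SAP 3.7.2 windows that visit by extension days. A sample taken about 30 days after the last filgotinib dose is thus an extension value. For a man who stops without entering the extension, the same 30 days belong to the double-blind phase. Under Amendment 1, placebo responders no longer have this visit, and open-label filgotinib men have theirs after the extension (SAP 3.7.2), so the columns do not share the same early sampling.

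**3. Size, with assumed inputs.** Let p be the proportion with an abnormality that emerged on blinded drug, q the fraction persisting into the extension, and r the new rate among the rest.

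- Reported = pq + (1 − pq)r; new only = (1 − pq)r.
- p = 10%, q = 50%, r = 5%: pq = 0.05. Reported = 0.05 + 0.95 × 0.05 = 9.75%; new only = 4.75%.
- Low corner, p = 5%, q = 25%: pq = 0.0125. Reported = 0.0125 + 0.9875 × 0.05 = 6.2%; new only = 4.9%.
- High corner, p = 20%, q = 100%: pq = 0.20. Reported = 0.20 + 0.80 × 0.05 = 24.0%; new only = 4.0%.

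**4. Effect on the contrast between sequences.** The rule applies to every column, so both sides must be modelled. Take p = 10% in both, r = 5% on Standard of Care and r = 10% on open-label filgotinib, all assumed; the new rates differ by 5.0 points.

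- q = 50% in both: 0.05 + 0.95 × 0.10 = 14.5% against 9.75%, a gap of 4.75 points.
- q = 80% on continued filgotinib: 0.08 + 0.92 × 0.10 = 17.2% against 9.75%, a gap of 7.45 points.

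The gap can shrink slightly or widen, depending on persistence rates that the documents do not give.

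**The case against.** The strongest case against is that this is a labelling matter in a descriptive table. SAP 8.2 plans no formal testing of laboratory data, and the sequences are not randomised groups, since they depend on Week 13 response. The filgotinib to Standard of Care column names the earlier exposure and is not pooled with placebo to Standard of Care. By-subject listings flag graded values, and the Grade 3 or 4 listing carries a man's full history for the test, so onset can be traced. The all-grade table is produced only at the final analysis. For continued filgotinib, a pre-study baseline is a reasonable measure of cumulative exposure. All of this stands and limits the weight of the point. It does not make the label accurate: listings do not correct a table, and the Grade 3 or 4 and marked tables are not confined to the final analysis.

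SAP 8.2.2.1 also speaks of the relevant baseline when that value is missing, which might suggest one baseline per phase. None is defined anywhere in the SAP.

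Three stronger readings are tempting and unsupported:

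- A reader might infer that carry-over narrows the difference between open-label filgotinib and Standard of Care. The open-label column carries over too, and step 4 shows that either direction is possible.
- A reader might take these tables to be the only long-term laboratory comparison. SAP 8.2.1 also gives values and changes by sequence and visit, and SAP 8.2.3 gives liver thresholds.
- A reader might say that each such abnormality is counted once as an adverse event and twice as a laboratory finding. Protocol 7.5 says laboratory abnormalities are usually not recorded as adverse events.

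**Conclusion.** The point holds as one of definition. SAP 8.2.2.1 and 8.2.2.2 count a persisting double-blind abnormality again as emerging in the extension, in all three sequences, and nothing elsewhere in the SAP prevents it. The label is least accurate for the two Standard of Care sequences. For filgotinib non-responders the extension also takes in the sample 30 days after filgotinib.

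How often this happens, and which way it moves any comparison between sequences, is unknown. The percentages above rest entirely on assumed inputs and show only that the effect could be anywhere from small to most of a reported count: 1.25 of 6.2 points at the low corner, 20 of 24 at the high corner. The primary and secondary semen endpoints are not touched. The correction is worth making because it is cheap and the present counts do not mean what their label says.

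**What to change.** In SAP 8.2.2.1 to 8.2.2.3:

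- Keep the current row for all three sequences, but label it *worsened from pre-study baseline, observed in the extension phase*.
- For all three sequences, add one row per test for a grade above both the pre-study baseline grade and the last double-blind-phase grade. Requiring both avoids counting a mere return to the pre-study grade. Add the same row for marked abnormalities, with the three-grade rule still applying.
- Base statements about what emerged in the extension on the new row.
- Footnote that, in the filgotinib to Standard of Care sequence, values within 30 days of the last filgotinib dose may reflect filgotinib. The new row alone does not deal with an abnormality first seen at that visit.

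The stricter definition should not replace the main row for the Standard of Care sequences alone. With the step 4 inputs at equal persistence, that would set 14.5% against 4.75%, a gap of 9.75 points where the new rates differ by 5.0. Keeping the current row also retains abnormalities that persist after filgotinib stops, which are safety information in their own right.

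The cost is one derived reference grade from data already held and one extra row per test. No visit or procedure changes.
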